12.4.3 Other statistical/analytical issues

12.4.3.1 Discontinuations and missing data

Missing 3-month MHGS data will be imputed as no change.

13 DATA HANDLING AND RECORDKEEPING

By signing and dating the CRF, or electronic signature of the electronic case report form (eCRF) if an Electronic Data Capture (EDC) system is used, the investigator will confirm that all investigations have been completed and conducted in compliance with the clinical study protocol, and that reliable and complete data have been entered into the CRF.

All data required by this clinical study protocol are to be recorded on CRFs, or eCRFs, as soon as possible. If paper-based, entries on the CRF must be legible and made with a blue or black ballpoint pen: pencils are not permitted. The monitor is not allowed to make entries into CRF or eCRF.

For paper-based CRFs, it is not permitted to erase, overwrite, or use correction fluid or tape on the CRF. If corrections are necessary, an authorized member of the investigator's staff will enter them in the following manner: the wrong entry will be crossed out with a single line (although it must remain legible) and the correct entry will be placed next to it. Corrections will be initialed, dated, and (if necessary) explained (e.g., corrections concerning AEs or the primary variable). Corrections that become necessary after collection of original CRF data sheets have to be documented on Data Clarification Forms (DCFs) and signed by the principal investigator (PI).

All data required by this clinical study protocol are to be entered into an EDC system if applicable, and a validated database, which applies to both paper-based and EDC systems.

If corrections in the subject diary or subject MHQ are necessary, the subject should be instructed to make a correction by drawing only a single line through the error, leaving the incorrect entry legible. The subject should date and initial the correction. The investigator should not make any changes to these documents.

Essential documents at the investigational site include but are not limited to:

- (1) Subject files
- (2) Subject identification code list
- (3) A copy of the study protocol and any amendments
- (4) Investigator's copies of the CRFs, DCFs forms, and any associated subject-related source data
- (5) Signed ICFs
- (6) Copies of all direct correspondence with the IRB and with the regulatory authority(ies), and with the Sponsor
- (7) Copies of hand photographs

(8) Copies of IP disposition records

Essential documents should be retained per applicable regulations and as instructed by the study Sponsor. Study documents may not be destroyed by study site personnel prior to the end of the required retention period of 25 years. The PI or the institution must inform the Sponsor in due time if the PI leaves the institution during the retention period. This rule also applies when the institution closes within the retention period.

14 PUBLICATION POLICY

The publication policy will be in accordance with the investigator agreement with the PI as executed prior to initiation of the investigational site.

# 1. Introduction

This study, a post approval study (PAS), is being conducted to satisfy a condition of the June 4, 2015, PMA-S (P050052/S049) approval of Radiesse® injectable implant indicated for hand augmentation to correct volume loss in the dorsum of the hand. This study will provide safety and effectiveness data in subjects with more severe volume loss than those subjects evaluated in the pre-market study. The pre-market (Merz protocol #P110607) study cohort excluded subjects with baseline grade 4 hands.

Radiesse® dermal filler was demonstrated to be safe and effective in the pre-market study for treatment of hands with moderate to severe dorsal volume loss. On the validated Merz Hand Grading Scale (MHGS), these were hands rated as grade 2 or grade 3 at baseline, or before treatment. With the Food and Drug Administration (FDA) approval of Radiesse® for treatment of these hands, it is anticipated that patients with MHGS grade 4 hands will seek treatment. Subjects will receive an initial Radiesse® hand treatment and have the opportunity to receive up to 3 repeat treatments over 2 years of follow-up.

# 2. Study Design

This is a prospective, open-label 2 year post approval study in up to 250 subjects to evaluate the safety and effectiveness of Radiesse® implantation for very severe volume loss in the dorsum of the hands in MHGS grade 4 subjects. Two groups will be enrolled with approximately 125 subjects in each group. Group A will consist of subjects with baseline MHGS grade 4 hands and Group B will consist of subjects with baseline MHGS grade 2 or grade 3. These subjects will be followed for two years with follow-up visits at 2 weeks, and at 1, 3, 6, 12, 18, and 24 months. At 6, 12, and 18 months, all subjects will be given the option of having a re-treatment. For those receiving re-treatment, an additional 72 hr follow-up telephone call will be made as well as a one month post re-treatment office visit. This results in the potential to have 7, 13, and 19 month follow-up data.

The primary safety endpoint will be evaluated at the 6 month time point comparing Group A with Group B.

### 3. Sample Size Estimation

Analysis of the primary safety endpoint will be based on a non-inferiority hypothesis test comparing the 6- month rate of device/injection-related severe AEs in the MHGS grade 4 subjects (Group A) versus the MHGS grade 2 and grade 3 subjects (Group B). Based on the pre-market study data, an expected rate of severe adverse events is 17% for both groups, and the test will be based on a 12% non-inferiority margin. This margin allows for adequate power of the planned hypothesis test with a reasonable sample size and will provide

assurance that the severe AE rate in the MHGS grade 4 subjects is not unacceptably higher given the expected benefit in these subjects. The test will be based on a one-sided Farrington-Manning likelihood score test of binomial proportions at a one-sided 0.05 alpha level. A maximum of 250 subjects with MHGS grades 2, 3 and 4 at baseline (at least 50% with both hands rated MHGS 4) will be enrolled in at least 5 sites and a maximum of 12 sites in the US. Allowing for some attrition, a total of 244 subjects (122 in each group) at 6 months will provide approximately 80% power to conduct the hypothesis test. Based on an expected attrition rate of 5% per year, a minimum of 225 evaluable subjects are required to provide 2-year follow-up data.

# 4. Randomization and Blinding

#### 4.1.Randomization

This study is not randomized. Subjects are enrolled directly into Groups A or B based on their baseline MHGS grade and are all treated with Radiesse®.

#### 4.2.Blinding

This is an open label study and as such subjects and treating physicians are not blinded. However the site evaluator will be blinded in the sense that he/she will not have access to previous ratings for subjects participating in the study and will also be blinded as to whether or not a subject has had repeat treatment(s). To ensure that the blind is maintained, subjects will have their upper body and face hidden behind a barrier screen with only their hand visible to the masked evaluator. Subjects will be asked to remain silent during the MHGS evaluation process. Masked evaluators will not be allowed to discuss treatment schedules with treatment investigators and study staff at the site, and will not enter data on case report forms that contain information that would break the blind.

### 5. Analysis Populations

### 5.1.Safety Evaluation Set (SES)

The SES is the subset of all subjects who were exposed to study device at enrollment.

#### 5.2.Per Protocol Set (PPS)

The PPS is the subset of subjects in the SES without major protocol deviations. Examples of a major protocol deviation would be absence of Radiesse® hand

treatment or receiving an exclusionary hand procedure during the study. Major protocol deviations will be determined at a data review meeting prior to database lock.

#### 6. Study Endpoints

#### 6.1. Primary Safety

6-month rate of device/injection-related severe adverse events.

#### 6.2. Secondary Safety

24 month rate of device/injection-related severe AEs. Hand function testing at baseline, study exit, and other collected time points.

### 6.4. Secondary Effectiveness

MHGS at 3-months after initial treatment

MHGS at 3-months following retreatment for those receiving retreatment.

GAIS at 3-months after initial treatment.

GAIS at 3-months following retreatment for those receiving retreatment.

Merz Hand Grading Scale PAS for Grade 4 Subjects – Statistical Analysis Plan Ver. 2.0 Date: Feb. 12, 2019

#### 7. Analysis

All endpoints will be analyzed using the SES population.

If the PPS differs from the SES, the analysis of the primary safety endpoint (including that by subgroups) will be performed on the PPS, too, for sensitivity. The enrollment table as well as the table on demographics will be repeated for the PPS (for description of this population).

7.1. Primary Safety Endpoint

The primary safety endpoint analysis will be based on a non-inferiority hypothesis test. Stated in terms of the null and alternate hypothesis, this is as follows:

Ho (null):  $P_A - P_B \ge 12\%$  vs

Ha (alternate): PA – PB < 12%

Where PA and PB are the percentages of subjects in Groups A and B who experience a device/injection-related severe adverse event by 6 months. Percentages will be calculated using the number of subjects experiencing at least one device/injection related severe treatment emergent adverse event (TEAE) by six months posttreatment as the numerator divided by the number of subjects in the SES (PPS) population with six month follow-up data.

TEAEs are defined as adverse events with onset or worsening after the first injection of Radiesse.

The test will be based on the Farrington-Manning likelihood score test. Testing will be done by constructing a one-sided 95% confidence interval using the Farrington-Manning method. If the upper 95% confidence bound around  $P_A - P_B$  is less than 12%, Ho will be rejected in favor of Ha, thus demonstrating non-inferiority, otherwise the Ho will be accepted.

# 7.2. Secondary Safety Endpoints

The number and percentage of subjects with at least one device/injection-related severe TEAE within 24 months of initial treatment as well as the number of events will be presented by group and in total. Percentages will be calculated using the number of subjects experiencing at least one device/injection related severe TEAE by 24 months

post-treatment as the numerator divided by the number of subjects in the SES population with 24 month follow-up data. The difference between the two proportions of subjects in groups A and B is calculated and presented together with a one-sided exploratory 95%-CI constructed via the Farrington-Manning likelihood method.No formal hypothesis testing will be done for this endpoint.

Hand-function data will be summarized descriptively and compared to baseline. Hand-function data were evaluated in relation to the incidence of a significant MHQ change or report(s) of severe difficulty performing activities with the hand(s) or severe loss of sensation in the hand(s) since previous visit. Correlation will be plotted between two hand-function test investigators for the first 10 subjects enrolled at each site. Differences between sites in hand-function results will be summarized descriptively and compared to baseline.

### 7.4. Additional Safety Analyses

The number and percentage of subjects experiencing physician reported TEAEs as well as the number of events itself will be reported for the following time periods:

- following initial treatment but occurring before retreatment,
- following month 6 retreatment but occurring before further retreatment,

- following month 12 retreatment but occurring before further retreatment,
- following month 18 retreatment but occurring before further retreatment.

The same will be done for subject-reported TEAEs.

Further, both, physician- and subject-reported TEAEs, will be analysed by maximum severity, by maximum duration and by number of treatments. Physician-reported TEAEs will additionally be analysed by maximum relationship.

In case of missing diary entries, the duration of a subject-reported TEAE will be calculated as follows:

- a. If the subject misses ONE day of diary entry, it is assumed that they had the event during that day they "forgot". The event will be counted as one TEAE then.
  - *i.* Example= Bruising reported on days 1, 2, 4, 5 and no diary entry on day 3; this would be a 5 day bruise of one TEAE
  - *ii.* Example= Swelling reported on days 2, 4, 5, 7 and no diary entry on day 3 or 6; this would be a 6 day swelling of one TEAE
- b. If the subject misses TWO OR MORE days of diary entry, it is assumed that they did NOT have the event during the 2 days they "forgot," and two unique TEAEs will be counted.
  - *i.* Example= Swelling reported on days 2, 3, 6, 7, 8 and no diary entry on days 4 and 5; this would be one TEAE of swelling lasting 2 days and one TEAE of swelling lasting 3 days (two unique subject-reported TEAEs)
  - *ii.* Example= Redness reported on days 1, 2, 3, 4, 7,8 and no diary entry on days 5 and 6; this would be one TEAE of redness lasting 4 days and one TEAE of redness lasting 2 days (two unique subject-reported TEAEs)

Differences between percentages of subjects with physician reported TEAEs in groups A and B will be presented together with exploratory 95% confidence intervals. The same will be done for subject-reported adverse events.

In addition, the number and percentage of subjects experiencing serious physician reported TEAEs as well as the number of events itself will be reported.

Kaplan-Meier time to event analyses will be performed for physician-reported adverse events.

The number and percentage of subjects with at least one device/injection-related severe TEAE over the course of the study as well as the number of events will be presented by group and in total. Percentages will be calculated using the number of subjects experiencing at least one device/injection related severe TEAE over the course of the study as the numerator divided by the number of subjects in the SES population. The difference between the two proportions of subjects in groups A and B

is calculated and presented together with a one-sided exploratory 95%-CI constructed via the Farrington-Manning likelihood method. In addition, a Kaplan-Meier time to event analysis will be performed. For subjects experiencing multiple events, the time to the first event will be used in this analysis. Subjects who do not experience a device/injection related severe adverse event until their 24 month visit will be censored at their 24 month follow-up time. Subjects withdrawing or lost to follow-up prior to their 24 month visit who have not experienced an event will be censored at their time of last known follow-up visit.

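### SAP 7.4 gives physician-reported TEAE percentages by treatment period with no common window or stated denominator, so the four percentages can differ through period length alone

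*SAP*

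**What the plan says.** SAP 7.4 tabulates the number and percentage of subjects with physician-reported TEAEs, and the number of events, in four periods. The first is "following initial treatment but occurring before retreatment" and the last is "following month 18 retreatment but occurring before further retreatment"; the middle two are built the same way from the Month 6 and Month 12 retreatments. No end day, person-time or denominator is given for this table.

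Retreatment is optional. SAP 2 states: "At 6, 12, and 18 months, all subjects will be given the option of having a re-treatment". The footnotes to Protocol Table 2 leave the decision to the treating physician and the subject.

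The event definition is broad. SAP 7.1 states: "TEAEs are defined as adverse events with onset or worsening after the first injection of Radiesse". Protocol 10 has AEs recorded from consent to the last visit, so unrelated events also count.

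The other planned displays are these:
- Physician- and subject-reported TEAEs "will be analysed by maximum severity, by maximum duration and by number of treatments", and "Physician-reported TEAEs will additionally be analysed by maximum relationship". Neither is stated to be by period.
- "Kaplan-Meier time to event analyses will be performed for physician-reported adverse events". A second Kaplan-Meier analysis covers device/injection-related severe events, and there "For subjects experiencing multiple events, the time to the first event will be used in this analysis". Neither is stated to restart at each injection.
- SAP 7.9 describes the retreatment schemes and injected volumes.
- Protocol 12.4.2 has event numbers and percentages reported by visit. SAP 7.4 does not repeat this, and SAP 8 does not list it as dropped.

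**The concern.** The Protocol Synopsis and Protocol 5.1 make the safety of multiple retreatments a secondary objective, with the hypothesis that retreatment brings no new safety concerns. The by-period table is the SAP's most direct by-injection display of physician-reported events for that objective. SAP 8 also drops the repeated-measures models that the protocol said might be used to describe time trends.

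Readers will compare the four rows. A longer period collects more background events at the same underlying risk, and the Month 18 period is nominally always the shortest. Differences between rows then mix any effect of retreatment with period length, and length depends on who chose to be retreated and when.

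**Working it through.** The plan gives no figure for this table, so there is none to reproduce. The period lengths follow from the schedule. The percentages are illustrations, because the documents give neither retreatment uptake nor by-period event risks.

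**1. Period lengths.** With yes or no at Months 6, 12 and 18 and follow-up to Month 24, there are eight retreatment patterns. Listing them gives these possible nominal lengths in months:
- initial: 6, 12, 18 or 24
- Month 6: 6, 12 or 18
- Month 12: 6 or 12
- Month 18: 6

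Visit windows and dropout blur these lengths.

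**2. Model.** Let *r* be the background risk per 6 months and *a* the acute risk after an injection, both the same after every injection. Over *k* six-month blocks the risk of at least one event is f(k) = 1 − (1 − a)(1 − r)^k. Let *u* be the uptake at each visit, independent of risk and of earlier choices, with no dropout. The denominator is assumed to be subjects who received that injection. Then:
- initial = u·f(1) + (1−u)u·f(2) + (1−u)²u·f(3) + (1−u)³·f(4)
- Month 6 = u·f(1) + (1−u)u·f(2) + (1−u)²·f(3)
- Month 12 = u·f(1) + (1−u)·f(2)
- Month 18 = f(1)

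**3. Numbers put in.** For r = 0.10 and a = 0, f(1) to f(4) are 0.100, 0.190, 0.271 and 0.3439. At u = 0.5:
- initial = 0.0500 + 0.0475 + 0.0339 + 0.0430 = 0.174
- Month 6 = 0.0500 + 0.0475 + 0.0678 = 0.165
- Month 12 = 0.050 + 0.095 = 0.145
- Month 18 = 0.100

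The other rows come the same way (%):

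| r | a | u | Initial | Month 6 | Month 12 | Month 18 |
|---|---|---|---|---|---|---|
| 10% | 0 | 50% | 17.4 | 16.5 | 14.5 | 10.0 |
| 10% | 0 | 80% | 12.2 | 12.1 | 11.8 | 10.0 |
| 10% | 50% | 50% | 58.7 | 58.3 | 57.2 | 55.0 |
| 10% | 50% | 80% | 56.1 | 56.1 | 55.9 | 55.0 |
| 20% | 0 | 50% | 32.5 | 31.2 | 28.0 | 20.0 |

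(The 57.2 is 57.25 before rounding.) True risk per injection is equal across each line. At u = 100% every entry in a line equals f(1).

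**4. Direction.** With uptake of 90%, 30% and 30% at the three visits, r = 10% and a = 0, the rows are 11.8/20.3/16.3/10.0%. Here the Month 6 and Month 12 rows look worse than the initial row at equal risk.

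**5. Denominator.** If all SES subjects were the denominator, the first line of the table would be multiplied by 1, 0.5, 0.5 and 0.5 and read about 17.4/8.3/7.2/5.0%. Later rows fall further simply because fewer subjects received those injections.

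**6. Sampling error.** Take 250 subjects in the initial row and 250·u in the Month 18 row, treat the rows as independent, and use SE = √[p₁(1−p₁)/n₁ + p₂(1−p₂)/n₂]. For initial minus Month 18:
- a = 50%, u = 80%: gap 1.1 points, SE = √(0.561×0.439/250 + 0.55×0.45/200) = 4.7 points
- a = 50%, u = 50%: gap 3.7 points, SE = √(0.587×0.413/250 + 0.55×0.45/125) = 5.4 points
- a = 0, u = 50%: gap 7.4 points, SE = √(0.174×0.826/250 + 0.10×0.90/125) = 3.6 points

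**7. Check of the remedy.** Every injection is nominally followed by at least 6 months. A common 6-month window therefore gives f(1) in all four rows: 10.0% throughout for r = 10% and a = 0, and 55.0% throughout for a = 50%.

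**The case against.** The strongest reply is that the table is descriptive, no test between periods is planned, and other material already helps. By-visit reporting under Protocol 12.4.2, with visits about one month after each injection (Months 1, 7, 13 and 19), comes close to a 30-day window. Subject-reported TEAEs share a 30-day diary after every treatment. SAP 7.9 will show how many subjects were retreated and when. Protocol 4.3 names bruising, swelling and redness as risks, so acute events are expected, and with mostly acute events the gap may lie within sampling error. The SAP mock shells were not in the text reviewed, and the section numbering passes from 7.2 to 7.4, so a per-period analysis elsewhere cannot be excluded.

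Most of this stands, and it limits the point. It does not remove it. By-visit reporting is not carried into SAP 7.4, the diary does not cover physician-reported events, and neither Kaplan-Meier analysis is stated to restart at an injection. Length bias also remains in the table when it is smaller than the sampling error. Protocol 12.4.2 does refer to follow-up time, but for the two MHGS groups and not for treatment periods.

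A reader might infer more than the documents support:
- *That the table always flatters retreatment.* The Month 18 row tends to look lower, but with uneven uptake the Month 6 and Month 12 rows can look worse (step 4).
- *That the 10% no-acute figures are a ceiling.* They are not: 20% background risk widens the gap at 50% uptake from 7.4 to 12.5 points.
- *That retreatment safety cannot be judged.* New types of event remain visible whatever the period length.

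**Conclusion.** The point holds in a limited form. Following SAP 7.4 as written gives four crude percentages over periods nominally lasting 6-24, 6-18, 6-12 and 6 months, and these can differ when the true risk per injection is the same. The period lengths come from the documents. The size rests on assumed uptake, assumed risks and an assumed denominator. At 10% background risk, the initial row exceeds the Month 18 row by 7.4 points at 50% uptake and 2.2 points at 80% with no acute events, and by 3.7 and 1.1 points with 50% acute risk. The gap is larger with higher background risk and nominally nil at full uptake. The missing denominator is a second ambiguity in the same table. The primary 6-month endpoint is untouched. The change is worth making because it is cheap and the table serves a stated objective.

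**What to change.** Keep the planned table and state its denominator as the subjects who received that injection. For physician-reported TEAEs, add the percentage with an event in a common window after each injection, for example 30 days, and up to 6 months but ending no later than the next injection. Footnote that the first cycle has extra Week 2 and Month 3 assessments, which give more opportunity to record events. Showing each retreatment cycle beside the same subjects' first cycle is optional. If data have already been reviewed, label the addition post hoc.

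The cost is SAP table definitions and some programming. Protocol 10 already requires AE start and stop dates, and treatment visits are recorded, so no new data are needed. The downside is that events after the window need a separate listing.

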VI), by initial and repeat injection volumes, and by study site by injection volume. In these analyses, subjects will be dichotomized based on injection volume less than or greater than or equal to the median injection volume. This will be done by hand (initial total injection volume per hand) and by subject (initial total injection volume by subject). Injection volumes will be recorded separately for the right hand and the left hand of each subject in the CRF for each treatment administered.

Subgroup analyses will be based on logistic regression models for the primary endpoints as a function of the subgroups, and with the appropriate interaction term. For example, for models comparing the MHGS groups by subgroup, model terms will include the MHGS group, subgroup term, and a term for the interaction of MHGS group and subgroup. Similarly, for the analysis of study site by injection volume, model terms will include MHGS group, study site, dichotomized injection volume, and the corresponding two and three way interaction terms. Analyses by hand will be based on generalized estimating equation models to account for correlations. A p-value of less than 0.05 for the appropriate interaction term will be considered statistically significant. Any such finding will result in additional exploratory analyses to understand possible causes and the clinical significance

Data from the baseline MHGS4 and baseline MHGS2-3 groups will be analyzed separately and in aggregate via descriptive statistics in addition to the above hypothesis test, with appropriate treatment of the follow-up time of each group.

Frequency tables (counts and percentages) and their confidence intervals (based on the binomial distribution) will be presented.

Hand function data will be summarized descriptively and compared to baseline. Hand function data will be evaluated in relation to

eport(s) of severe difficulty performing activities with the hand(s) or severe loss of sensation in the hand(s) since previous visit. Correlation will be plotted between 2 hand function test investigators for the first 10 subjects enrolled at each site. Differences between sites in hand function results will be summarized descriptively and compared to baseline.

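### Neither long-term A-B difference in severe related events accounts for censored follow-up, although a Kaplan-Meier analysis with censoring is already planned

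*SAP*

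**What the plan says.** SAP 7.4 reports, by group, the percentage of subjects who had any "device/injection related severe TEAE over the course of the study as the numerator divided by the number of subjects in the SES population". No length of follow-up is required, and SAP 5.1 sets none either: "The SES is the subset of all subjects who were exposed to study device at enrollment". The A-B difference of these two percentages is then "presented together with a one-sided exploratory 95%-CI constructed via the Farrington-Manning likelihood method".

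The same paragraph continues: "In addition, a Kaplan-Meier time to event analysis will be performed". Its censoring rule is explicit. "Subjects withdrawing or lost to follow-up prior to their 24 month visit who have not experienced an event will be censored" at the last known visit, and subjects still event-free at Month 24 are censored there. No between-group difference or confidence bound is specified from these curves.

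SAP 7.2 has a second long-term A-B difference, for the 24-month secondary endpoint, also with a one-sided exploratory Farrington-Manning interval. Its denominator is limited to SES subjects who have 24-month data.

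Protocol 12.4.2 says that the two groups will be described separately and together "with appropriate treatment of the follow-up time of each group", and it names Kaplan-Meier for the incidence of adverse events over time. On attrition, SAP section 3 reads "Based on an expected attrition rate of 5% per year" and asks for at least 225 evaluable subjects at two years. Protocol section 7 says that leavers are not replaced.

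**The concern.** A Farrington-Manning interval on a difference of proportions treats each subject as one fully observed binomial trial. Under SAP 7.4 a subject followed for one month and a subject followed for 24 months carry the same weight. If the first leaves without an event, the remaining 23 months are scored as event-free. Subjects who had a severe related event before leaving are counted correctly, so the problem lies with event-free leavers only.

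Late follow-up matters here because retreatment is offered at Months 6, 12 and 18, so exposure continues after some subjects may have gone, and the safety of repeated treatment is a stated secondary objective. The crude percentage understates the 24-month risk in both groups, and more so in the group that loses more subjects. The groups are not randomized, and Protocol section 7 says that Group A hands might receive higher volumes, so unequal attrition is possible. If A lost more, the difference would move towards no excess risk in grade 4 hands; if B lost more, it would move the other way. The documents predict neither.

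**Working it through.** **The plan's own figure.** 250 × 0.95² = 225.6, which matches the 225 in SAP section 3. This is the only attrition figure given, and it is not split by group.

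**Assumptions.** The documents give no 24-month event rate and no attrition by group, so the following are assumed:
- risk per injection p of 10% to 17% (17% is the plan's 6-month planning rate, reused here as an upper value);
- injections at 0, 0.5, 1 and 1.5 years, with retreatment uptake u of 50% to 100%;
- events occurring at injections, and dropout at annual rate a, unrelated to risk.

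**Formula.** With r₁ = p and r₂ = r₃ = r₄ = p·u, the probability of a first event at injection k is dₖ = rₖ × Π(1 − rⱼ) over j < k. The 24-month risk is Σdₖ. The expected crude percentage is Σdₖ(1 − a)^tₖ.

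**Worked case, p = 0.10, u = 100%.**
- Risk: 0.1000 + 0.0900 + 0.0810 + 0.0729 = 34.4%.
- Crude at a = 5% (retention 1, 0.9747, 0.95, 0.9259): 0.1000 + 0.0877 + 0.0770 + 0.0675 = 33.2%.
- Crude at a = 15% (retention 1, 0.9220, 0.85, 0.7837): 0.1000 + 0.0830 + 0.0689 + 0.0571 = 30.9%.
- At 15% in A and 5% in B with equal true risk, the difference is 30.9 − 33.2 = −2.3 points, where the truth is 0.

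**All four corners** (percentages; shifts in points, taken before rounding):

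| p | u | Risk | Crude, a = 5% | a = 10% | a = 15% | Level shift at 5% | A-B shift, 10% v 5% | A-B shift, 15% v 5% |
|---|---|---|---|---|---|---|---|---|
| 10% | 50% | 22.8 | 22.2 | 21.6 | 21.0 | −0.6 | −0.6 | −1.2 |
| 10% | 100% | 34.4 | 33.2 | 32.1 | 30.9 | −1.2 | −1.2 | −2.3 |
| 17% | 50% | 36.4 | 35.5 | 34.5 | 33.6 | −0.9 | −0.9 | −1.9 |
| 17% | 100% | 52.5 | 50.9 | 49.2 | 47.6 | −1.7 | −1.7 | −3.3 |

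With equal risk and equal attrition the A-B shift is 0 in every row.

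**Sensitivity to event timing.** Let F be the 24-month risk and μ = −ln(1 − a).
- Constant hazard: λ = −ln(1 − F)/2 and crude = λ/(λ + μ) × (1 − exp(−2(λ + μ))). At F = 25% the crude percentage is 23.8, 22.7 and 21.5 for a = 5%, 10% and 15%, so the A-B shift is −1.2 (10% v 5%) and −2.3 (15% v 5%). If the true risks are 29% and 17%, with 5% attrition in both groups, the 12.0-point difference is seen as 27.6 − 16.2, or 11.5 before rounding.
- 80% of events straight after the first injection and the rest uniform over 24 months: crude = F × [0.8 + 0.2 × (1 − exp(−2μ))/(2μ)]. At F = 25% this gives 24.75, 24.51 and 24.27, so the shifts are only −0.2 and −0.5.
- Lower uptake: p = 17% and u = 25% in the injection model gives −0.5 and −1.0.

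**The case against.** The crude percentage is a legitimate description. It states how many treated subjects had an event during the study and does not claim to be the risk had everyone stayed. In the injection model a leaver receives no further study injections, so the missed events belong to treatments that were never given. The analysis is labelled exploratory, and the subject-flow table in SAP 7.6 will show who left and when. All of this stands. It is why the crude figures should be kept and why the point is minor.

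Four stronger readings are tempting, and the documents do not support them.

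- **That the all-SES difference is the only long-term comparison.** SAP 7.2 supplies another, with a different denominator. It does not close the gap, because it leaves subjects without 24-month data out of the denominator instead of using the follow-up they contributed.
- **That the SAP departs from the protocol without listing the change in section 8.** Protocol 12.4.2 asks for descriptive statistics that respect follow-up time and for Kaplan-Meier, and the SAP plans Kaplan-Meier. Neither document promises a between-group difference from the curves.
- **That subjects leaving because of adverse events would hide harm, and that Kaplan-Meier would cure this.** A severe related event before leaving is already in the numerator. If milder events drive dropout and predict later severe ones, censoring is informative and Kaplan-Meier is biased too.
- **That the shift uses up a sizeable part of the 12-point margin.** That margin belongs to the 6-month primary test. This interval is not tested against any margin.

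The upper end of the range also leans on reusing 17% as the risk at each of four injections, which gives a 24-month risk of 52.5%. Nothing in the documents supports a risk that high.

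**Conclusion.** The point holds as a low-priority improvement. Neither long-term A-B difference accounts for censored follow-up, while the analysis in the same paragraph that does so yields no contrast.

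At the planned 5% per year in both groups, each group's percentage is about 0.6 to 1.7 points low under assumed risks of 10% to 17% per injection and uptake of 50% to 100%. The A-B difference is then unbiased if the risks are equal, and is pulled slightly towards zero if they differ. If attrition were 10% to 15% per year in A against 5% in B, the difference would shift by about −0.2 to −3.3 points. The small end applies when events cluster at the first injection, and the large end when every subject is retreated each time at the highest assumed risk. All of these rates are assumptions except the 5%. The primary 6-month test and its sample size are not affected.

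**What to change.** In SAP 7.4, add from the planned Kaplan-Meier analysis each group's 24-month cumulative incidence (read at a stated day), the A-B difference, and a one-sided 95% upper bound: the difference + 1.645 × √(SE_A² + SE_B²), with Greenwood standard errors. Name this as the main over-the-study comparison. Keep the crude percentage and its Farrington-Manning interval, labelled as unadjusted for follow-up.

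The cost is a sentence or two in the SAP and one extra output. The curves and the censoring rule already exist, and no new data are needed. The stated rate will be slightly higher and the bound slightly wider. Kaplan-Meier assumes that dropout is unrelated to risk, so it reduces the bias but does not remove it where that fails; the SAP should say so next to the estimate.
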